**WEIGHT**

10. A body mass index (BMI) within range of 18.5 - 35 kg/m^2 (inclusive) at screening.

**SEX**

11. Male and female subjects

**Males:**

Male subjects with female partners of child bearing potential must comply with the following contraception requirements in [Appendix 6](#).

**Females:**

A female subject is eligible to participate if she is not pregnant (as confirmed by a negative serum human chorionic gonadotrophin [hCG] test), not lactating, and at least one of the following conditions applies:

- a. Non-reproductive potential defined as:
  - Pre-menopausal females with one of the following:
    - Documented tubal ligation

 
• Documented hysteroscopic tubal occlusion procedure with follow-up confirmation of bilateral tubal occlusion
 
• Hysterectomy
 
• Documented Bilateral Oophorectomy
 
 
• Postmenopausal defined as 12 months of spontaneous amenorrhea in questionable cases a blood sample with simultaneous follicle stimulating hormone (FSH) and estradiol levels consistent with menopause (refer to laboratory reference ranges for confirmatory levels). Females on hormone replacement therapy (HRT) and whose menopausal status is in doubt will be required to use one of the highly effective contraception methods (see Appendix 6) if they wish to continue their HRT during the study. Otherwise, they must discontinue HRT to allow confirmation of post-menopausal status prior to study enrolment.
 
b. Reproductive potential and agrees to follow one of the options listed in the Modified List of Highly Effective Methods for Avoiding Pregnancy in Females of Reproductive Potential (FRP) (see Appendix 6) from 30 days prior to the first dose of study medication and until at least 30 days after the last dose of study medication and completion of the follow-up visit.
 
The Investigator is responsible for ensuring that subjects understand how to properly use these methods of contraception.

--

INFORMED CONSENT
------------------

12. Capable of giving signed informed consent as described in Section 10.2 which includes compliance with the requirements and restrictions listed in the consent form and in this protocol.
--

## 5.2. Exclusion Criteria

A subject will not be eligible for inclusion in this study if any of the following criteria apply:

CONCURRENT CONDITIONS/MEDICAL HISTORY (INCLUDES LIVER FUNCTION AND QTc INTERVAL)
--

- |  |
|--|
| 
 
1. Subject with a positive anti-double stranded deoxyribonucleic acid (DNA [anti-dsDNA]) and confirmed diagnosis of systemic lupus erythematosus (SLE).
 
2. Subject with current history of Suicidal Ideation Behaviour (SIB) as measured using the Columbia Suicide Severity Rating Scale (C-SSRS) or a history of attempted suicide.
 
3. An active infection, or a history of infections as follows: 
 
• Hospitalisation for treatment of infection within 60 days before first dose (Day 1).
 
• Currently on any suppressive therapy for a chronic infection (such as pneumocystis, cytomegalovirus, herpes simplex virus, herpes zoster and
 
 
 
 |
|--|

atypical mycobacteria).

- Use of parenteral (IV or intramuscular) antibiotics (antibacterials, antivirals, antifungals, or antiparasitic agents) for an infection within 60 days before first dose.
  - A history of opportunistic infections within 1 year of screening (e.g. pneumocystis jirovecii, CMV pneumonitis, aspergillosis). This does not include infections that may occur in immunocompetent individuals, such as fungal nail infections or vaginal candidiasis, unless it is of an unusual severity or recurrent nature.
  - Recurrent or chronic infection or other active infection that, in the opinion of the Investigator might cause this study to be detrimental to the patient.
  - History of TB, irrespective of treatment status.
  - A positive diagnostic TB test at screening defined as a positive QuantiFERON-TB Gold test or T-spot test. In cases where the QuantiFERON or T-spot test is indeterminate, the subject may have the test repeated once, but they will not be eligible for the study unless the second test is negative. In cases where the QuantiFERON or T-spot test is positive, but a locally-read follow up chest x-ray, shows no evidence of current or previous pulmonary tuberculosis, the subject may be eligible for the study at the discretion of the Investigator and GSK Medical Monitor.
4. QTc >450msec or QTc >480msec for subjects with bundle branch block at screening. The QTc is the QT interval corrected for heart rate according to either Bazett's formula (QTcB), Fridericia's formula (QTcF), or another method, machine or manual over read.
- The specific formula that will be used to determine eligibility and discontinuation for an individual subject should be determined and documented prior to initiation of the study. In other words, several different formulae cannot be used to calculate the QTc for an individual subject and then the lowest QTc value used to include or discontinue the subject from the trial. For purposes of data analysis, QTcB, QTcF, another QT correction formula, or a composite of available values of QTc will be used as specified in the Reporting and Analysis Plan (RAP).
5. ALT >2xULN and bilirubin >1.5xULN (isolated bilirubin >1.5xULN is acceptable if bilirubin is fractionated and direct bilirubin <35%) at screening.
  6. Current active or chronic history of liver or biliary disease (with the exception of Gilbert's syndrome or asymptomatic gallstones).
  7. Current or history of renal disease or estimated glomerular filtration rate (GFR) by Chronic Kidney Disease Epidemiology Collaboration equation (CKD-EPI) calculation <60 mL/min/1.73m^2 at screening.
  8. Hereditary or acquired immunodeficiency disorder, including immunoglobulin deficiency.
  9. A major organ transplant (e.g., heart, lung, kidney, liver) or hematopoietic stem cell/marrow transplant.
  10. Any planned surgical procedures including surgical joint procedures (e.g., intra-articular, tendon sheath, or bursal corticosteroid injections) during the study.
  11. A history of malignant neoplasm within the last 5 years, except for adequately treated


non-metastatic cancers of the skin (basal or squamous cell) or carcinoma in situ of the uterine cervix that has been fully treated and shows no evidence of recurrence.
 
12. Has undergone surgery including synovectomy or arthroplasty on the joint chosen for biopsy and/or magnetic resonance imaging (MRI).
 
13. The subject has a history of any other joint disease other than RA at the knee, wrist or ankle joint chosen for biopsy and/or MRI (e.g., gout, pseudogout, osteoarthritis).
 
14. Has undergone intra-articular corticosteroid injection, arthrocentesis or synovial biopsy on any joint within 6 weeks of screening.
 
15. A known allergy to lidocaine or other local anaesthetics (Note: only applies to subjects who consent for synovial biopsy procedures).
 
16. Contraindication to MRI scanning (as assessed by local MRI safety questionnaire) which includes but are not limited to:
 
 
• Intracranial aneurysm clips (except Sugita) or other metallic objects,
 
• History of intra-orbital metal fragments that have not been removed by a medical professional.
 
• Pacemakers or other implanted cardiac rhythm management devices and non-MR compatible heart valves,
 
• Inner ear implants,
 
• History of claustrophobia which may impact participation.
 

--

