#### 5.1. Inclusion Criteria

A subject will be eligible for inclusion in this study only if all of the following criteria apply:

AGE
1. Between 18 and 75 years of age inclusive, at the time of signing the informed consent.
TYPE OF SUBJECT AND DIAGNOSIS INCLUDING DISEASE SEVERITY
2. Subjects that do not have any medical conditions, other than moderate to severe RA that in the opinion of the Investigator put the subject at unacceptable risk or interfere with study assessments or integrity of the data. These medical conditions should be

stable at the time of screening and are expected to remain stable for the duration of the study.

3. Subject has had a confirmed diagnosis of rheumatoid arthritis according to the revised 2010 American College of Rheumatology/European League Against Rheumatism ACR-EULAR classification criteria.
4. Disease duration of  $\geq 12$  weeks (time from onset of patient-reported symptoms of either pain or stiffness or swelling in hands, feet or wrists) at screening.
5. Swollen joint count of  $\geq 4$  (28-joint count) and tender joint count  $\geq 4$  (28-joint count) at screening.
6. Subject has a DAS28 CRP disease activity score of  $\geq 3.2$  and CRP  $\geq 5.0$  mg/L ( $\geq 4.76$  nmol/L) at screening.
7. Subject must have received at least 12 weeks of non-biologic DMARD monotherapy or methotrexate (MTX)/DMARD combination therapy prior to screening AND must be on stable dose throughout the study.
8. Subject is naive to any biological therapies for RA

**OR**

Subject may have had previous exposure to a single anti-TNF biologic agent which was discontinued for reasons other than primary non-response more than 8 weeks (or 5 half lives whichever is longer) from first dose. **Note: Exposure to a single anti-TNF is not required in addition to Inclusion #7 above.**

9. For subjects who have consented to synovial joint biopsy:
  - a. Subject has an involved knee, wrist, or ankle suitable for biopsy, as assessed by a rheumatologist at screening.

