### 5.4. Withdrawal/Stopping Criteria

Subjects may be withdrawn from the study for any of the following reasons:

- A subject may withdraw from study treatment at any time at his/her own request, or may be withdrawn at any time at the discretion of the Investigator for safety, behavioural or administrative reasons. If a subject withdraws from the study, he/she may request destruction of any samples taken, and the Investigator must document this in the site study records. The reason for withdrawal should be documented in the Case Report Form (CRF).

- The Sponsor's request, for reasons such as significant protocol deviations or subject safety concern (and after discussion with the Investigator).
- If a subject is withdrawn from study treatment, this subject is also considered to be withdrawn from the study.
- Study is terminated by the Sponsor.

If a subject is withdrawn, the Sponsor may decide to replace that subject and this will be done through the Interactive Response Technology System (IRTS).

If a subject chooses to withdraw from the study after dosing then the Investigator must make every effort to complete the follow-up assessments detailed in the Time and Events Table (Section 7.1).

The following actions must be taken in relation to a subject who fails to attend the clinic for a required study visit:

- The site must attempt to contact the subject and re-schedule the missed visit as soon as possible.
- The site must counsel the subject on the importance of maintaining the assigned visit schedule and ascertain whether or not the subject wishes to and/or should continue in the study.
- In cases where the subject is deemed 'lost to follow up', the Investigator or designee must make every effort to regain contact with the subject (where possible, 3 telephone calls and if necessary a certified letter to the subject's last known mailing address or local equivalent methods). These contact attempts should be documented in the subject's medical record.
- Should the subject continue to be unreachable, only then will he/she be considered to have withdrawn from the study with a primary reason of "Lost to Follow-up".

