### 5.4.3.1. Study Treatment Restart or Rechallenge

Study treatment restart or rechallenge after liver chemistry stopping criteria are met by any subject participating in this study is not allowed.

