4. QTc >450msec or QTc >480msec for subjects with bundle branch block at screening. The QTc is the QT interval corrected for heart rate according to either Bazett's formula (QTcB), Fridericia's formula (QTcF), or another method, machine or manual over read.
- The specific formula that will be used to determine eligibility and discontinuation for an individual subject should be determined and documented prior to initiation of the study. In other words, several different formulae cannot be used to calculate the QTc for an individual subject and then the lowest QTc value used to include or discontinue the subject from the trial. For purposes of data analysis, QTcB, QTcF, another QT correction formula, or a composite of available values of QTc will be used as specified in the Reporting and Analysis Plan (RAP).
5. ALT >2xULN and bilirubin >1.5xULN (isolated bilirubin >1.5xULN is acceptable if bilirubin is fractionated and direct bilirubin <35%) at screening.
6. Current active or chronic history of liver or biliary disease (with the exception of Gilbert's syndrome or asymptomatic gallstones).
7. Current or history of renal disease or estimated glomerular filtration rate (GFR) by Chronic Kidney Disease Epidemiology Collaboration equation (CKD-EPI) calculation <60 mL/min/1.73m^2 at screening.
8. Hereditary or acquired immunodeficiency disorder, including immunoglobulin deficiency.
9. A major organ transplant (e.g., heart, lung, kidney, liver) or hematopoietic stem cell/marrow transplant.
10. Any planned surgical procedures including surgical joint procedures (e.g., intra-articular, tendon sheath, or bursal corticosteroid injections) during the study.
11. A history of malignant neoplasm within the last 5 years, except for adequately treated

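### Exclusion 5 joins its ALT and bilirubin limits with 'and', so a raised ALT alone, at any height, passes the criterion, as does a raised bilirubin alone

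*Protocol*

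**What the plan says.** The lead-in to Section 5.2 makes each numbered exclusion sufficient alone: "A subject will not be eligible for inclusion in this study if any of the following criteria apply". Criterion 5 is one item holding two laboratory limits: "ALT >2xULN and bilirubin >1.5xULN (isolated bilirubin >1.5xULN is acceptable if bilirubin is fractionated and direct bilirubin <35%) at screening". Amendment 4 keeps the same core wording, "ALT >2xULN and bilirubin >1.5xULN", and the same parenthesis.

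Two other criteria bear on the liver in general terms. Exclusion 6 covers "Current active or chronic history of liver or biliary disease", apart from Gilbert's syndrome and silent gallstones. Inclusion 2 keeps out conditions "that in the opinion of the Investigator put the subject at unacceptable risk" and asks that conditions be "stable at the time of screening and are expected to remain stable for the duration of the study". Exclusion 24 deals with hepatitis B and C serology. None of these sets an ALT value.

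On treatment, Appendix 2 (Section 12.2) lists six liver stopping events, one of which is ALT of at least 5xULN with no bilirubin condition. Section 5.4.3.1 then adds: "Study treatment restart or rechallenge after liver chemistry stopping criteria are met by any subject participating in this study is not allowed".

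**The concern.** An entry rule should keep out subjects who already sit at the level where treatment must stop. Criterion 5 does not do this for ALT. Section 5 forbids deviations from the criteria and insists that they be followed as specified, so a site that applies the text literally is following instructions.

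Three things are at stake:

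- **Avoidable exposure.** A subject whose ALT was raised before the first dose can be given an investigational drug that Section 4.6.1 says might impair methotrexate clearance. Methotrexate is permitted up to 25 mg per week (Table 1).
- **Permanent discontinuation for a pre-existing finding.** The stopping rules do not ask whether the raised ALT was there at entry.
- **Blurred liver safety data.** Safety is the primary objective and the active TID group is small, so one liver event whose origin is unclear carries weight.

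**Working it through.** The protocol states no figure to reproduce, so the check sets the wording of criterion 5 against the stopping thresholds.

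**Step 1. Truth table.** Let A be ALT above 2xULN and B be bilirubin above 1.5xULN, both at screening. The literal rule excludes when A and B both hold. The alternative rule excludes when A or B holds, unless bilirubin alone is raised, has been fractionated, and is less than 35% direct.

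| Screening result | Literal 'and' | 'Or' with parenthesis |
|---|---|---|
| ALT 3xULN, bilirubin normal | passes | excluded |
| ALT 6xULN, bilirubin normal | passes | excluded |
| ALT normal, bilirubin 2xULN, 50% direct | passes | excluded |
| ALT 3xULN, bilirubin 2xULN | excluded | excluded |

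Under the literal rule the first three patterns pass. The second is already above the absolute ALT stopping level. The third is one that the parenthesis plainly means to exclude.

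**Step 2. What the parenthesis shows.** It grants isolated raised bilirubin a conditional pass. Under 'and', isolated bilirubin can never meet the criterion, so there is nothing to make an exception from. The exception works only if each limit excludes alone. Nearby criteria with alternative conditions use 'or' (Exclusions 4 and 7) or semicolons (Exclusion 23).

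**Step 3. Stopping thresholds (Appendix 2, Amendment 3 text).**

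- Absolute: ALT at or above 5xULN.
- Persistence: ALT at or above 3xULN for four weeks or more.
- ALT at or above 3xULN with raised bilirubin.
- ALT at or above 3xULN with raised INR.
- ALT at or above 3xULN that cannot be monitored weekly.
- ALT at or above 3xULN with symptoms.

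All 6 need a raised ALT, and only 1 of the 6 also needs a raised bilirubin. The entry rule therefore ignores ALT alone, while the stopping rules are built on it.

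**Step 4. Distance from entry to stopping.** With 'or', the highest ALT passing at screening is 2xULN.

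- To 3xULN: 3 / 2 = 1.5-fold rise.
- To 5xULN: 5 / 2 = 2.5-fold rise.

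With literal 'and' and bilirubin at or below 1.5xULN there is no ceiling. A subject entering at 5xULN or more needs no rise to meet the absolute stop. One who stays at 3xULN meets the persistence rule once four weeks have passed.

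**Step 5. Timing.** Section 7.1 schedules the eligibility check at screening only. Chemistry is drawn before dosing on Day 1, but nothing makes that result a condition of entry. The first chemistry after dosing starts is Day 8 plus or minus 3 days, that is 8 - 3 = Day 5 to 8 + 3 = Day 11. An ALT persisting at 5xULN or more would meet the stopping rule by then at the latest.

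**Step 6. Weight of one event (illustration).** Table 5 gives an upper credible limit of 19.5% for 0 events in 16 and 28.7% for 1 in 16. If one stop rooted in a pre-existing ALT elevation were counted as an event on active treatment, it would move that limit by 28.7 - 19.5 = 9.2 percentage points.

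**The case against.** The best defence is practical. The parenthesis makes the intent so clear that many sites will read 'or' anyway. An ALT of 5xULN or more is also the value least likely to be waved through: it would have to get past Exclusions 6 and 24, the investigator's judgement under Inclusion 2, and the investigator's duty under Section 7.3 to assess out-of-range results. Once a subject is on treatment, the stopping rules act, and Section 5.4 lets the sponsor replace a withdrawn subject. This stands as a limit on impact. The more realistic gap is moderate isolated elevation, roughly 2 to 5xULN. But the backstops are partial and carry no ALT number, and stopping or replacing a subject comes after the exposure.

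Four stronger readings are tempting, and the protocol does not support them:

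- **That the subject is lost to the study.** Section 5.4 does say "If a subject is withdrawn from study treatment, this subject is also considered to be withdrawn from the study". Appendix 2, however, specifically lets a subject permanently off treatment after a liver event stay for the protocol's follow-up assessments. The firm consequence is loss of treatment.
- **That the correction guarantees ALT of no more than 2xULN at dosing.** The limit applies at screening, which may be up to 30 days before Day 1, and ALT can move in between.
- **That ALT is the only gap.** Literal 'and' also lets through isolated bilirubin with a direct fraction of 35% or more.
- **That liver tests are the main safeguard against drug interactions.** Section 4.6.1 lists them beside concomitant-medication review, clinical monitoring and methotrexate PK sampling. The pre-dose Day 1 chemistry also gives a baseline, which helps attribution but does not remove the difficulty.

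**Conclusion.** Criterion 5 is wrong as written. Read literally, it sets no upper limit on isolated ALT and admits a bilirubin pattern that its own parenthesis rejects. No other criterion supplies an ALT ceiling.

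Its size is best given as thresholds: no ceiling now, against 2xULN at screening once corrected. The 1.5-fold and 2.5-fold distances are ratios between limits and do not measure risk. The protocol gives no frequency of isolated ALT elevation among those screened, so no expected number of affected subjects is claimed.

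The conclusion assumes that sites apply the text literally, as Section 5 requires. It also takes the six stopping rows from the Amendment 3 text. The revision chronology describes Amendment 4 as reinstating only Exclusion 23 and the haematologic stopping criteria, so those rows are assumed unchanged there.

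**What to change.** In Section 5.2, criterion 5, replace 'and' with 'or' between the two limits, so that ALT above 2xULN or bilirubin above 1.5xULN at screening excludes. Keep the parenthesis on isolated bilirubin as it is. Make the same edit in the Amendment 3 and the Germany-specific Amendment 4 texts.

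The cost is one word in two documents and possibly a few more screen failures. Section 5.3 already softens that by allowing one repeat of a failing laboratory test within the screening window. No assessment, visit or analysis changes.

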#### CONCOMITANT MEDICATIONS

17. The subject has received treatment with the therapies listed in Section 6.11.2, or changes to those treatments, within the prescribed timeframe. If in doubt, or the therapy is not listed please consult with the medical monitor.
 
 
• Other medications (including vitamins, herbal and dietary supplements) will be considered on a case-by-case basis, and will be allowed if in the opinion of the Investigator the medication will not interfere with the study procedures or compromise subject safety.
 

---

#### RELEVANT HABITS

18. History of alcohol or drug abuse that would interfere with the ability to comply with the study.

---

#### CONTRAINDICATIONS

19. History of sensitivity to any of the study treatments, or components thereof or a history of drug or other allergy that, in the opinion of the Investigator or Medical Monitor, contraindicates their participation.
 
20. Received a live or attenuated vaccine within 30 days of randomization OR plan to receive a vaccination during the study until 5 half-lives (or 2 days) plus 30 days after receiving GSK2982772.
 
21. Contraindication to gadolinium contrast agent in accordance with local guidelines.
 
22. The subject has participated in a clinical trial and has received an investigational

--

product within 30 days or 5 half-lives, whichever is longer before the first dose of study medication, or plans to take part in another clinical trial at the same time as participating in this clinical trial.

#### DIAGNOSTIC ASSESSMENTS AND OTHER CRITERIA

23. Haemoglobin <9 g/dL; haematocrit <30%, white blood cell count  $\leq 3,000/\text{mm}^3$  ( $\leq 3.0 \times 10^9/\text{L}$ ); platelet count  $\leq 100,000/\mu\text{L}$  ( $\leq 100 \times 10^9/\text{L}$ ); absolute neutrophil count  $\leq 1.5 \times 10^9/\text{L}$  at screening.
24. Presence of hepatitis B surface antigen (HBsAg), positive hepatitis C antibody test result at screening or within 3 months prior to first dose of study treatment. As potential for and magnitude of immunosuppression with this compound is unknown, subjects with presence of hepatitis B core antibody (HBcAb) should be excluded.
25. A positive serology for human immunodeficiency virus (HIV) 1 or 2 at screening.
26. Where participation in the study would result in donation of blood or blood products in excess of 500 mL within 3 months.
27. Exposure to more than 4 investigational medicinal products within 12 months prior to the first dose.

